A prospective randomized-controlled trial of custom-manufactured vs. off-the-rack (OTR) compression hosiery for initial management of venous disease

Study Short Title

Custom vs OTR compression hosiery for venous disease

B. Clinical Phase

Phase IV

C. Study Population

The study will include patients aged 18 and over who have CEAP classification 2-5 venous disease and require compression as definitive therapy or in preparation for ablation therapy.

D. Study Design

Prospective double-blinded, controlled randomized clinical trial with 2-armed parallel-group sequential design

E. Sample Size

200

F. Study Duration

2 years

G. Study device and Intervention Description

Subjects will be randomized into two groups: group A will receive custom-manufactured compression hosiery (Isobar compression garment), and group B will receive off-the-rack stockings (Sigvaris).

H. Primary Objective

To assess the efficacy of custom-manufactured compression hosiery compared to off-the-rack compression hosiery for improving patient satisfaction, health-related quality of life and compliance with prescribed compression therapy

I. Secondary Objectives

- *To identify subgroups that may benefit more from custom hosiery.*
- *To determine whether improved fit affects likelihood to progress to invasive treatment.*

VI. BACKGROUND AND SIGNIFICANCE

Currently available off-the-rack compression hosiery are manufactured in eight fixed sizes (S-XLFC) that cannot be varied in size over their length to accommodate unusual anatomic patterns (eg., small ankle with large calf or vice versa) and may not achieve a comfortable fit that meets the compression goal over a uniform distribution of the limb. The custom-fitted garment is manufactured specifically for each patient based on measurements taken with a 3-dimensional volumetric laser scan of the extremity, and can be sized individually to each limb. In addition to providing data to computer assisted design-enabled manufacturing equipment, the scan data can be downloaded for analysis and may be useful for identifying patients for whom custom stockings are most beneficial and may ultimately be useful for prediction compliance and patient satisfaction. We propose to scan all trial participants prior to randomization so we can assess this in a control group as well.

VII. PRIMARY OBJECTIVES

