The target population of our study will be comprised of patients that are 18 years-old and above that present to our group at The University of Texas Medical School at Houston with venous disease requiring treatment with compression.

Inclusion/Exclusion Criteria

Patients will be *eligible for the study if:*

- 18 years-old or older, and
- Ability to comprehend and sign an informed consent and complete study questionnaires
- Patient is participating in usual work and home activities with no changes anticipated for the duration of the study
- The use of compression stocking is prescribed in accordance with the usual practice and management of venous disorders
- The patient will confirm they are willing to pay for the compression stockings.

Patients will be *excluded from the study if:*

- The patient has a known allergy to any component of the stocking (latex, etc)
- The patient has non-venous source of pain in either leg that could, in the opinion of the investigator, confound the results of the study i.e. Neuropathy, Arterial insufficiency, Diabetes
- The patient is confined to bed
- The patient has uncontrolled Congestive Heart Failure
- The patient has acute dermatitis
- The patient has weeping dermatosis
- Patients with venous ulcers will be excluded.

Protocol Deviation:

- Patient is randomized but does not receive the correct treatment assignment

Withdrawal criteria:

- Voluntary: patients who had consented and enrolled in the trial will maintain their right to withdraw at any point during the study as explained in the informed consent.
- In case of unexpected/unpredicted events, the Principal Investigator and research staff may determine that patient meets criteria for withdrawal.

X. STUDY DEVICES

The Custom stocking, (Isobar Compression Garment) is an FDA Class 1 device. The control stocking (Sigvaris) is also an FDA Class 1 device. These devices are rated at 15 mmHg compression and are comparably priced.

XI. STUDY SCHEDULE

Expected start date after IRB Approval: Eligible to begin January 2017

Expected end date for enrollment: January 2019

Length of treatment-phase enrollment for each patient: 90 days

Length of follow-up for each patient: 90 days from initiation of compression for primary endpoint; six months for assessment of likelihood to receive follow-on ablation therapy.

XII. STUDY DESIGN/METHODOLOGY

This will be a single institution, prospective, blinded, randomized, controlled

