clinical trial with a 2-arm parallel-group design to assess the efficacy of custom-fitted compression hosiery vs off-the-rack compression hosiery.

The custom stockings take 2 weeks to manufacture. In order to maintain the blind, stockings will be procured by the UT CV Surgery purchasing personnel and distributed to the subjects in unmarked packaging within three weeks of randomization. Neither the prescribing physician nor the patient will know the treatment assignment.

Screened patients meeting the eligibility criteria will have a below-knee laser measurement scan, and will be randomized into one of the two study groups.

At the screening visit, patients will be evaluated for trial eligibility and the study will be explained. For eligible patients who wish to participate, informed consent will be obtained and the patient will receive history and physical exam and will complete baseline HRQoL and pain scale surveys. Volumetric scans will be performed and the data will be stored. Patients will be randomized by a study coordinator, and will be instructed to expect stockings in the mail within 3 weeks.

After stockings are dispensed, patient should call the office to inform the study nurse or coordinator of the day they are beginning therapy, and biweekly log will be kept as a measure of compliance.

Patients in the study should also complete the Brief Pain Inventory (BPI) before randomization (at baseline following enrollment), by phone during week six, and at clinical follow-up after completing 90 days of compression therapy. Additionally, patients will be assessed on their satisfaction at week six and at 90-day clinical follow-up. This

will be done using the 5-point satisfaction scale with 1 being “very dissatisfied” to 5 being “very satisfied”. The SF-12 HRQoL instrument will also be completed at enrollment, at six weeks and at 90-day follow-up. This will conclude the 90-day treatment period. Patients will be re-contacted at six months post-treatment to determine whether they are still using their stockings (or have replaced them) or have progressed to invasive treatment. After the six-month assessment, the study will be concluded and enrollment will be terminated.

Study Conduct

1. Screening

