
Randomization and allocation concealment will be performed by study personnel using a restricted-access randomization file. The sequence will be generated by a UT

statistician in a random permuted block design and copied to a secure drive accessible only to unblinded study personnel. At enrollment patients will be assigned a study ID number. The laser scan data will be identified by this study number and noted in the CRF. Depending on the group assignment, either an order for a custom pair of stockings will be generated and tagged to the scan data – which will then be transmitted to the manufacturer – or the appropriate pair of Sigvaris stockings will be procured. After two weeks, the stockings as allocated by randomization will be packed in unbranded packaging and mailed to the research subject by trackable means (UPS, FedEx, US Postal Service, etc.). The clinical personnel who assess the patients will not handle the hosiery and will not see it on the patient. The patient will not know whether the stockings are custom or off-the-rack, so the double masking will be maintained.

5. Baseline assessment

History, physical exam and review of symptoms will be conducted at enrollment and captured to an electronic case report form that will be implemented at UT in REDCap. The examining physician will draw a diagram of the involved veins for comparison with the 90-day examination. Pain assessment and HRQoL will be captured as described previously.

6. Follow-up

After the initiation visit is completed, the follow-up will be:

- i. Compression therapy per physician directive throughout 90 days with a compliance log to be kept bi weekly.*

- ii. *At 6 weeks questionnaire completion via phone.*
- iii. *At 90 days clinic follow-up and questionnaire completion*
- iv. *At six months after treatment initiation by telephone*

7. Termination of enrollment

Patient will be considered to have his/her enrollment terminated:

- i. *After completion of the six month telephone survey*
- ii. *If any medical/surgical/environmental condition develops that would affect or impair primary or secondary outcomes measurements results*
- iii. *If the study is terminated*
- iv. *If the patient dies*

8. Termination of Study

- i. *End of study period*
- ii. *Unanticipated safety problems that would make continuation unethical*
- iii. *If the trial does not look as though it can achieve its enrollment targets within two years*

XIII. ADVERSE EVENT REPORTING

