Patients enrolled in the trial will be instructed to report any unwanted effect at any time during the study. For this study, only adverse events that are directly related to the use of compression stocking will be reported. Expected adverse effects of compression therapy will be described to the patients during the screening/enrollment as well as in the informed consent process. Most adverse side effects are minor and may include rash, contact dermatitis, discomfort, lack of symptomatic relief, and in rare cases, local skin ischemia and breakdown.

Safety monitoring will include assessment of:

- i. Adverse Effects (AE)
- ii. Vital Signs
- iii. Wound healing status
- iv. Pain
- v. Satisfaction

All parameters will be closely monitored in a continuous manner, as part of our standard clinical care. Any abnormalities found will be promptly assessed and described in the patient's medical records. Patients will be instructed to call the clinic if problems arise, and will also be assessed at clinic visits. If need be, an immediate unscheduled visit shall be arranged if the patient so desires.

The PI will review AEs as they occur, and requirement for changes to the study design or device use will be determined on an ongoing basis. This study does not require a DSMB.

XIV. STATISTICAL ANALYSIS PLAN

A. Primary Outcomes

The trajectory of BPI, HRQoL and Patient Satisfaction scores at 45 and 90 days of treatment will be measured by mixed-effects linear models between the groups.

Appropriate score transformations will be performed as necessary to meet distributional assumptions of the tests. Randomization is expected to balance the groups with respect to pre-intervention risk factors.

Total time worn over 90 days as reflected in diary entries will be compared by Wilcoxon rank-sum test between the two groups..

A. Secondary Outcomes

[figure not shown]
Additional analyses will be performed to determine whether patient characteristics such as calf/ankle ratio and other measurements made using laser scan data show differential (interaction) effects in the custom-stocking group vs the off-the-rack group.

Progression to ablation will be measured as simple test of proportions (Fisher's Exact test) of those seeking ablative therapy in the custom vs OTR groups.

B. Sample Size Determination

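### The enrolment-termination rule removes patients because their outcomes would be affected, with no follow-up afterwards and no analysis as randomised, so it may bias the comparison

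*Combined protocol and SAP*

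**What the plan says.** Section XII, Study Conduct, item 7 (Termination of enrollment) lists four events that end a patient's enrolment. Three are the six-month telephone survey, the end of the study, and death. The fourth, item ii, is: "If any medical/surgical/environmental condition develops that would affect or impair primary or secondary outcomes measurements results".

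The Study Design/Methodology text uses the same term for the end of data collection: "After the six-month assessment, the study will be concluded and enrollment will be terminated". Section IX adds a discretionary route: "In case of unexpected/unpredicted events, the Principal Investigator and research staff may determine that patient meets criteria for withdrawal".

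Other text that bears on the scope of item ii:

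- Section C of the synopsis admits patients who "require compression as definitive therapy or in preparation for ablation therapy".
- An inclusion criterion in section IX reads "Patient is participating in usual work and home activities with no changes anticipated for the duration of the study".
- Section XIII names the expected effects of the stocking: "rash, contact dermatitis, discomfort, lack of symptomatic relief, and in rare cases, local skin ischemia and breakdown". It also states that "only adverse events that are directly related to the use of compression stocking will be reported".
- On masking, section XII, item 4 says: "The clinical personnel who assess the patients will not handle the hosiery and will not see it on the patient".

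Section XIV plans mixed-effects linear models for the Brief Pain Inventory (BPI), quality-of-life and satisfaction scores, a Wilcoxon rank-sum test on total hours worn over 90 days, and Fisher's exact test on progression to ablation. It names no analysis population and gives no missing-data rule.

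**The concern.** A patient's removal under item ii depends on something that happens after randomisation and would change the outcomes being compared. Read literally, any medical or surgical condition covers effects that the stocking itself can cause, such as contact dermatitis or skin breakdown. It also covers an ablation before day 90, which is a foreseen path for patients enrolled on the way to ablation. The trial's premise is that off-the-rack stockings may fit less comfortably, so unequal rates by arm are plausible on the protocol's own reasoning.

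If termination ends data collection, the patients who remain are no longer the randomised groups. The errors need not point the same way. Losing poor scorers from one arm makes that arm look better on scores, while shortened diaries make the same arm look worse on wear time. Because only stocking-related adverse events are reported, nothing requires the reasons for other terminations to be recorded by arm, so a reader could not judge the problem afterwards. Data that were never collected cannot be recovered at analysis.

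**Working it through.** **1. Does item ii end data collection?** The other three items in the list are all ends of participation, and the design text ties the end of enrolment to the last assessment. The natural reading is that an earlier termination means no later questionnaire, diary or call. Item ii does not say that data already collected are discarded.

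**2. Is there a safeguard elsewhere?** I found no text on follow-up after termination, intention-to-treat, or missing data. The nearest is in the secondary outcome measures, which describe ablation as a proportion compared between the randomised groups. That covers one outcome and does not say that terminated patients are followed or counted.

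**3. How large could the bias be?** The documents give no termination rates. All rates below are assumptions, with no true effect and 100 patients per arm as planned. OTR is given the higher rate; reversing the rates reverses the direction.

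*Scores.* Assume three visits, unit variance and equal correlation ρ between visits. The lowest fraction p of u = c·Y + √(1−c²)·e is removed, where Y is the score that drives removal and e is independent noise. The model is fitted by maximum likelihood with arm-by-visit means and an unstructured covariance. The table gives the bias at day 90 (OTR minus custom, in SD) for ρ = 0.3 / 0.5 / 0.7; simulation error is about 0.003.

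| Removed, OTR vs custom | What drives removal | After week 6 | Before week 6 |
|---|---|---|---|
| 15% vs 5% | day-90 score, c = 1 | 0.151 / 0.121 / 0.080 | 0.154 / 0.135 / 0.098 |
| 15% vs 5% | day-90 score, c = 0.5 | 0.073 / 0.056 / 0.033 | 0.076 / 0.067 / 0.044 |
| 10% vs 5% | day-90 score, c = 1 | 0.075 / 0.061 / 0.042 | 0.078 / 0.070 / 0.049 |
| 10% vs 5% | day-90 score, c = 0.5 | 0.038 / 0.028 / 0.016 | 0.036 / 0.035 / 0.022 |

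The bias is within 0.003 of zero if removal depends only on the observed week-6 score, and within 0.004 of zero at 10% vs 10%.

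An upper illustration is a complete-case comparison after removing the lowest fraction p, where the mean shifts by φ(z_p)/(1−p). That is 0.274 at 15% and 0.109 at 5%, a difference of 0.166 SD. For scale, the unadjusted standard error with 95 and 85 patients is √(1/95 + 1/85) = 0.149 SD.

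*Hours worn.* Assume a mean of 8 hours a day with SD 2 or 3. Terminated patients are still wearing the stocking, and their diary is cut at a uniformly random day and used as it stands. The Wilcoxon test at 5% then rejects as follows:

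- 15% vs 5%: 0.153 (SD 2) and 0.138 (SD 3), nearly always in favour of custom. Small changes to the simulation settings moved this between about 12% and 16%.
- 10% vs 5%: 0.080 and 0.070.
- 10% vs 10%: 0.045 and 0.048.

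*Ablation.* Let the true rate be q in both arms. A share p is terminated for reasons other than ablation and dropped, and these patients would have progressed k times as often as the arm average. The observed rate is (q − p·k·q)/(1 − p). With q = 0.30, custom at p = 0.05 and OTR at p = 0.15:

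- k = 1: 0.300 vs 0.300, no gap.
- k = 1.5: 0.2775/0.95 = 0.292 vs 0.2325/0.85 = 0.274, a gap of 1.9 points.
- k = 2: 0.270/0.95 = 0.284 vs 0.210/0.85 = 0.247, a gap of 3.7 points.

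For k = 2, the gap is 2.5 points at q = 0.20 and 5.0 points at q = 0.40.

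**The case against.** The strongest reply is that item ii is aimed at outside confounders. The stable-activities inclusion criterion supports that. Stocking effects have their own route in section XIII through adverse-event review and clinic visits, and progression to invasive treatment is an outcome, so it would be odd for it to end follow-up. The scope is indeed ambiguous. However, the wording does not impose the narrow reading, and a rule that staff can apply either way is itself a weakness. Where ablation is the trigger, ablation status is already known and only later scores are lost.

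Masked assessors limit arm-dependent judgement. They cannot prevent selection through effects that the stocking causes. The mixed model helps only as far as earlier scores explain the removal.

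The larger figures are stress cases, and that point stands. Section XIII calls most effects minor. At 10% vs 5% with correlation 0.5, a bias of 0.02 to 0.04 SD against a standard error of √(1/95 + 1/90) = 0.147 SD raises a nominal 5% false-positive rate only to between 5% and 6%. The ablation gaps of 1.9 and 3.7 points give exact Fisher rejection rates of about 4.8% and 7.3%, against 3.5% with no loss.

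The wear-time figure needs unequal termination among patients still wearing the stocking. Someone who stopped because of dermatitis has a truly short total. If terminated patients are instead dropped and termination is unrelated to hours, rejection stays near 5%.

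The score calculation assumes three visits for every instrument, whereas the protocol is inconsistent about which ones are given at week 6 and lists no satisfaction score among the baseline surveys in section XII. The range is therefore less certain for SF-12 and satisfaction. Finally, section XIII does have abnormalities described in the medical record, so some reasons may be recoverable, though not by a planned report per arm.

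**Conclusion.** The concern holds. As written, item ii selects patients out of follow-up on a post-randomisation condition tied to the outcomes, and nothing in the plan brings them back into the analysis. The documents support the statement that this may bias the comparison; they do not show that it will.

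The size runs from zero (equal loss of the same kind in both arms, or, for the mixed model, removal explained by observed scores) to about 0.15 SD on scores. That upper value is roughly one standard error of the treatment difference, at an assumed 15% vs 5% with the worst scorers removed. Values of 0.02 to 0.08 SD are more moderate illustrations. Hours worn and ablation lack the partial protection that the mixed model gives. The rates are assumptions throughout, and the direction is unknown. This should be corrected because the remedy is cheap and lost follow-up cannot be restored; confidence in the practical size is moderate.

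**What to change.** - Reword item 7(ii) so that an intercurrent condition, stopping the stocking, or an ablation does not end data collection. This concerns follow-up only and takes no position on treatment.
- Keep the scheduled week-6, 90-day and six-month contacts, and the diary while the stocking is worn, unless the patient withdraws consent or dies or the study ends. Align the discretionary withdrawal clause in section IX with this.
- Record the event, its date, and whether it is judged related to the stocking.
- State in section XIV that all patients are analysed in their assigned arm and that hours after the stocking is stopped count as zero.
- Add one sensitivity analysis that sets aside scores obtained after unrelated intercurrent conditions. This serves the purpose of item ii if outside confounders were what it meant.
- Report terminations and their reasons by arm.

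The cost is protocol wording and about three case-report-form fields; the visits and calls are already scheduled. The downside is slightly more noise in the 90-day scores from intercurrent conditions, which the sensitivity analysis addresses.

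### An undefined relatedness test decides which adverse events are reported, and no view of events by arm is planned, so the safety stopping criterion is not assured complete trial-level data

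*Combined protocol and SAP*

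**What the plan says.** Section XIII opens with a broad request: "Patients enrolled in the trial will be instructed to report any unwanted effect at any time during the study". The next sentence applies a filter: "For this study, only adverse events that are directly related to the use of compression stocking will be reported". The same section lists adverse effects, vital signs, wound healing, pain and satisfaction as monitored items. It states "Any abnormalities found will be promptly assessed and described", and the place named for that description is the patient's medical record. On oversight it says "The PI will review AEs as they occur" and "This study does not require a DSMB"; section XVII repeats that no board is needed, given the low risk of the devices.

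In section XII, Study Conduct, item 8.ii gives as one ground for ending the study: "Unanticipated safety problems that would make continuation unethical". It attaches no threshold and does not say what information is to be examined. Item 4, on masking, says: "The clinical personnel who assess the patients will not handle the hosiery and will not see it on the patient". Section XV.C concedes that subjects may face risks not yet known. Section XIV (Statistical Analysis Plan) contains no analysis of adverse events.

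**The concern.** Relatedness is normally a property recorded about an event. Here it decides whether the event is reported at all, and it is decided case by case before anyone could see a pattern. For an expected effect such as a rash under the stocking, that may do little harm. For an effect nobody foresaw, the first few cases are the ones most likely to be judged unrelated. Those cases are what item 8.ii would need.

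The comparison also matters. The two garments differ in how they fit the leg, so a harm peculiar to one of them would show as an imbalance between arms. Review of single events as they arise, with no view by arm, is poorly placed to reveal an imbalance. If events left out of trial reporting are held only in clinical notes, it may not be possible to reassemble them consistently afterwards.

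**Working it through.** The plan states no adverse event rate, safety threshold or safety power, so there is no figure to reproduce. The check is to follow one event through the text.

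1. **Entry.** The patient may report anything (section XIII). The event is then reported by the trial only if it is directly related to stocking use (the next sentence of XIII).
2. **Who decides, and how.** No section defines directly related or names who makes the call. The only named reviewer of adverse events is the PI.
3. **Where an excluded event goes.** Section XIII sends abnormalities to the medical record. The case report form content described in Study Conduct items 4 and 5 is the baseline history, examination, symptoms, pain and quality of life, plus a note of the scan data. No adverse event form is described.
4. **Who looks across events.** The PI reviews events as they occur. There is no board, and no interim or final table of events by arm in section XIII, XIV or XVII.
5. **What depends on the result.** Item 8.ii, and any later statement about the comparative safety of the two garments.

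Steps 1 to 4 do not secure a complete set of events, by arm, for step 5.

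**Can a direction of bias be claimed?** This illustration uses assumed values throughout; the documents supply only the 100 per arm. Let the device-caused risk be d (5% in one arm, 15% in the other) and the background risk b = 20% in both. Let the filter catch a fraction s of device events and wrongly attribute a fraction f of background events.

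- All events recorded: risk = 1 − (1 − d)(1 − b). This gives 1 − 0.95 × 0.80 = 24.0% and 1 − 0.85 × 0.80 = 32.0%. Difference 8.0 points; ratio 1.33.
- Fairly accurate filter (s = 80%, f = 10%): risk = 1 − (1 − sd)(1 − fb). This gives 1 − 0.96 × 0.98 = 5.9% and 1 − 0.88 × 0.98 = 13.8%. Difference 7.8 points; ratio 2.32.
- Poor filter (s = 50%, f = 30%): 1 − 0.975 × 0.94 = 8.4% and 1 − 0.925 × 0.94 = 13.1%. Difference 4.7 points; ratio 1.56.

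Dividing each difference by its standard error, √[(p₁(1 − p₁) + p₂(1 − p₂))/100], gives 8.0/6.32 = 1.26 for all events, 7.84/4.18 = 1.88 for the fairly accurate filter and 4.7/4.36 = 1.08 for the poor one. On these assumptions the filter sharpens the contrast in one case and weakens it in the other, so no direction can be claimed.

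**The case against.** The strongest case against the point is proportionality. Both garments are commercially available Class 1 devices prescribed in usual practice, and reporting only related events is a stated choice. Safety information is not absent: unwanted effects are solicited, abnormalities are charted, unscheduled visits are offered, and the sentence on PI review is not limited to related events. Item 8.ii is a qualitative judgement that can be exercised without a full dataset. All of this stands. It rules out saying that the stopping criterion has no data or cannot work. It also supports having no board. It does not explain why unrelated-seeming events should be left out of the trial's own reporting when the cost of keeping them is small. If the filter was meant to govern only onward reporting and not what is recorded, the text does not say so, and no adverse event form is described either way.

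Two stronger readings are tempting.

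- A reader might infer that relatedness is judged by staff who are not allowed to see the stocking on the leg. The documents do not assign the judgement to anyone. Item 4 of Study Conduct restricts seeing the garment on the patient, not examining the bare leg, so the skin effects that section XIII lists remain visible. Masking also protects a relatedness judgement from bias by arm.
- A reader might infer that the filter pulls any arm difference in harm toward zero. That does not follow: a reasonably accurate filter that removes background events can make the contrast clearer, and section XIV plans no test of adverse events in any case.

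**Conclusion.** The point holds in a limited form. An undefined judgement, assigned to no one, is the condition for an adverse event to be reported. Other abnormalities are described only in the medical record, and nothing provides for seeing events by arm. The safety criterion in item 8.ii is therefore not assured complete trial-level data, and excluded events may not be recoverable for the comparison of the two garments. This rests on reading reported as covering the trial's own record, which is the natural reading when no other record of adverse events is described.

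No size can be put on the loss without event rates and a known accuracy of attribution, and the documents give neither. The documents do not support a claim that the criterion is unworkable or that arm differences are biased in a particular direction. This is a cheap improvement worth making.

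**What to change.** Replace the filtering sentence in section XIII with wording such as:

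> All adverse events reported or observed from first wear to last contact are recorded in the REDCap CRF; relatedness to the stocking, judged by a named reviewer masked to arm, is recorded as an attribute and does not determine whether the event is recorded.

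State the criteria the reviewer uses. In section XIV, add a descriptive table by arm of all events and of related events, with leg and skin events shown separately. The UT statistician, whose role already includes generating the allocation sequence, can prepare it. It should be kept from assessors and be available when item 8.ii is considered. Recording everything keeps both the all-event and the related-event views, so nothing is lost relative to the present rule.

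The cost is protocol wording, a short form in the existing database, a simple table, and entry of some unrelated events for 200 patients. No extra visits or staff are needed.

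### Safety monitoring is described as continuous, but apart from the day-90 clinic visit no scheduled contact after mailing is specified to ask about, or examine for, adverse events or skin harm

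*Combined protocol and SAP*

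**What the plan says.** Section XIII (Adverse Event Reporting) names the expected harms: rash and contact dermatitis, discomfort, failure to relieve symptoms and, rarely, ischemia or breakdown of the skin. It lists five safety parameters: adverse effects, vital signs, "Wound healing status", pain and satisfaction. Of these it says: "All parameters will be closely monitored in a continuous manner, as part of our standard clinical care". Patients are told to report unwanted effects and to telephone if a problem arises. They are also to be assessed when they attend clinic, and an unscheduled visit can be arranged at their wish.

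Section XII gives the schedule. Under Study Conduct item 4 the stockings are "packed in unbranded packaging and mailed to the research subject by trackable means"; the Methodology text has them "distributed to the subjects in unmarked packaging within three weeks of randomization". The patient telephones to give the start day, and a "biweekly log will be kept as a measure of compliance". Study Conduct item 6 then lists "At 6 weeks questionnaire completion via phone", a clinic visit with questionnaires at 90 days, and a telephone contact at six months. The Methodology text gives the purpose of that last contact: "to determine whether they are still using their stockings (or have replaced them) or have progressed to invasive treatment".

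On entry criteria, section IX states: "Patients with venous ulcers will be excluded". It also excludes acute dermatitis and weeping dermatosis.

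**The concern.** The monitoring sentence promises more than the schedule provides. Vital signs and wound status cannot be examined by telephone, and the documents name no clinic visit between mailing and day 90, or after day 90. The two calls have stated content, and neither includes a question about adverse events or skin.

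Two things are at stake. The first is the safety record. Section XVII dispenses with a DSMB, so the safeguards are the principal investigator's review of events as they occur and the option to stop the study for unanticipated safety problems. Both work only on events that reach the team.

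The second is the interpretation of a primary outcome. Compliance is total hours worn over 90 days. A patient who wears the stocking less because of dermatitis, and does not report it, contributes low hours. No field is described that would separate this from inconvenience or poor fit. In a trial about fit, that distinction is of direct interest.

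**Working it through.** The plan gives no safety figure to reproduce, and the point depends on no power or error rate. The check sets the contacts against the safety list and then does day arithmetic.

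**Contacts and their stated content**

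| Contact | Source | Stated content | Adverse-event or skin item specified? |
|---|---|---|---|
| Baseline visit, before wear | XII, Study Conduct 1 and 5 | history, physical examination, vital signs, BPI, SF-12, vein diagram | no leg-skin record named |
| Patient's start-day call | XII, Methodology | start date | no |
| Biweekly log | XII, Methodology; Study Conduct 6 | compliance | no |
| Week-six call | VII; XII | BPI in both sections; satisfaction and SF-12 in XII only | no |
| Day-90 clinic visit | XII, Study Conduct 5 and 6; XIII | questionnaires; examination compared with the baseline vein diagram; general assessment at clinic visits | general assessment only; no skin check named |
| Six-month call | XII | continued or replaced stockings; invasive treatment | no |

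**Safety parameters against that schedule**

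- Pain and satisfaction: collected at week six and day 90.
- Vital signs and wound healing: day 90 is the only scheduled opportunity after mailing.
- Adverse effects: listed, with no method or timing for asking. The routes given are patient report and assessment at clinic visits.

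**Day arithmetic**

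Inputs: manufacture takes 2 weeks and delivery occurs within 3 weeks of randomization (XII). Assumptions: randomization at the baseline visit, wear starting on receipt, week six as day 42 of wear, and six months as 182 days.

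- Scheduled examinations between first wear and day 90: 0.
- Baseline examination to day-90 examination: 14 + 90 = 104 days, to 21 + 90 = 111 days.
- Week-six call to day 90: 90 − 42 = 48 days.
- Day 90 to the last call, timed from initiation (Study Conduct 6): 182 − 90 = 92 days.
- Day 90 to the last call, timed from the end of treatment (Methodology text): 182 days.

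The last two results differ because section XII times the six-month call in two ways.

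**The case against.** The strongest reply is proportionality. Both stockings are FDA Class 1 devices prescribed under usual practice, and safety is neither an objective nor an endpoint. Spontaneous reporting plus a clinic visit may be a reasonable level of surveillance. That can justify having no DSMB and no extra visits. It does not justify describing as continuous a schedule with one examination after mailing.

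Several stronger readings are tempting, and the documents do not support them.

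- *A reader might infer that skin harm is caught only if patients volunteer it.* Section XIII says patients are also assessed at clinic visits, and Study Conduct item 5 refers to an examination at 90 days. An event visible then could be found without a report.
- *A reader might infer that the calls ask nothing about harm.* The week-six call collects pain and, in section XII, satisfaction. Both are listed safety parameters, and discomfort and lack of relief are named adverse effects. What is absent is an adverse-event or skin question.
- *A reader might infer that the wound-healing item is empty because patients with ulcers are excluded.* The exclusion holds at entry. Skin breakdown during wear is a named risk and could be followed under that item, and the adverse-effects heading covers rash and dermatitis. The item should stay.
- *A reader might infer that the reason for stopping wear is always lost.* Abnormalities that come to notice go into the medical record. The loss concerns unreported events.
- *A reader might call the period after day 90 half (90/180) or two-thirds (180/270) of exposure.* The treatment phase is 90 days, and the documents do not say how many patients continue wearing the stockings.
- *A reader might cite the bound for zero events in 100 patients per arm,* 1 − 0.05^(1/100) = 2.95% (one-sided 95%). This is a sample-size limit even under complete capture, and better questioning would not change it.

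There are also other touchpoints: the start-day call, the log, and an initiation visit mentioned in Study Conduct item 6 without content. None is described as an adverse-event check.

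**Conclusion.** The point holds in a limited form. From mailing to day 90, and again after day 90, no scheduled contact is specified to ask about adverse events or to examine the skin. In those periods, detection of rash, contact dermatitis, ischemia and breakdown rests on patient-initiated reports. At day 90 a persisting event could be found and a resolved one missed.

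The gap between scheduled examinations is about 104 to 111 days, and no examination follows day 90. These lengths rest on wear starting on receipt and on the schedule being followed as written. The documents give no event rates, so the number of events missed cannot be estimated.

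No planned primary or secondary comparison is invalidated. The consequences are a weaker safety record and a compliance outcome whose low values may have no recorded cause. The correction is cheap and worth making.

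**What to change.** 1. Add one fixed item set, worded identically in both arms, to the week-six call, the day-90 visit and the six-month call. It should ask whether, since the last contact, the patient has had rash, dermatitis, skin breakdown or other signs of the skin risks named in section XIII, or any other unwanted effect, and whether wear was stopped or reduced because of it. Record the answers on the case report form, before any judgement about relatedness to the stocking.
2. Add leg-skin condition to the safety list, recorded at baseline and at the day-90 examination already planned. Keep the wound-healing item alongside it.
3. In section XIII, replace the claim of continuous monitoring with these time points plus spontaneous reporting at any time.
4. Reconcile the two timings of the six-month call in section XII (from initiation, or after the end of treatment).

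The cost is a short form at contacts that already exist, with no additional visits. Elicited minor complaints will raise the adverse-event count in both arms, so the counts should be reported as solicited. A week-six question about reduced wear might itself influence later wear; identical wording and timing keep the prompt the same in both arms. Management of any reported problem stays with the clinicians.
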